I will test the central hypothesis that visceral adiposity plays a key role in the pathogenesis of diabetes and that EMPA may positively impact glucose homeostasis in viscerally-obese individuals using functional studies of glycerol metabolism in hepatic gluconeogenesis using a well-validated nuclear magnetic resonance (NMR) spectroscopy platform. The rationale of this project is to utilize emerging technology to investigate potential mechanisms underlying diabetes risk related to excess VAT and explore the potential beneficial effects of EMPA on these pathways. I will achieve the scientific objectives of this application by pursuing the following two specific aims:

1. Elucidate the relationship between VAT mass and glucose homeostasis by measuring enrichment of glycerol in blood glucose by NMR spectroscopy. Here we will measure the differential enrichment of exogenous ¹³C₃-labeled glycerol vs. adipose-derived glycerol in blood glucose among non-diabetic obese adults with high vs. low VAT using a single venous blood sample.

Hypothesis 1: Participants with high VAT will have greater adipose contribution of glycerol and therefore lower ¹³C₃ glycerol enrichment compared with age, sex, and BMI-matched participants with low VAT.

2. Determine the effect of EMPA on glucose homeostasis in non-diabetic obese adults with differing VAT mass. In this aim we will measure changes in the enrichment of ¹³C₃ glycerol in response to treatment with EMPA or placebo among age, sex, and BMI-matched participants stratified by high vs. low VAT.

Hypothesis 2: ¹³C₃ glycerol enrichment will increase from baseline (signifying less contribution from adipose tissue) among EMPA-treated participants with high VAT, with no change in EMPA-treated low VAT or placebo-treated participants.

2. Background:

Diabetes mellitus type II is the consequence of insulin resistance and pancreatic beta cell failure resulting from a variety of metabolic insults, one of which is excess body adiposity/obesity. In the

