The rationale of this project is to utilize existing technology to investigate the impact of excess visceral adiposity on glycerol metabolism in hepatic gluconeogenesis in obese adults without diabetes and to explore the effects of treatment with EMPA on visceral adiposity related glucose homeostasis. Our hypothesis is that among individuals with excess visceral adipose tissue, high lipolytic turnover results in excess adipose-derived glycerol shunting to the liver and hyperactive gluconeogenesis. This phenomenon will be reflected in a relatively low enrichment of dietary (labeled) glycerol when analyzed by NMR spectroscopy when compared with obese individuals with low visceral adiposity. We also hypothesize that $^{13}\text{C}_3$ glycerol enrichment will increase from baseline (signifying less contribution from adipose tissue) among EMPA-treated participants with high VAT, with no change in EMPA-treated low VAT or placebo-treated participants.

3. Concise Summary of Project:

Study Population:

Obese (BMI ≥ 30 kg/m²) participants who are referred, or enrolled in the DHS, without prevalent type 2 diabetes who have previously undergone VAT imaging by MRI³³ or DXA³⁴ or will have an MRI as part of this study will be recruited. Participants with high VAT will be selected and matched (age, sex, BMI) with an equal number of low VAT participants, defined by the highest and lowest age-and-sex stratified decile of VAT in the study population. Individuals with prevalent dyslipidemia or liver disease that could influence $^{13}\text{C}_3$ glycerol enrichment will be excluded. Recruitment is highly likely to be successful given that >450 DHS participants have been recruited to participate in additional mechanistic studies to date.

Exposure variables:

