[U- $^{13}\text{C}_3$] glycerol 50 mg/kg (obtained from Cambridge Isotopes, Andover, MA) will be given to participants to drink. It is non-radioactive and non-toxic. There is no known risk to drinking glycerol. Ingestion of this item is similar to drinking a commercial sugar sweetened beverage. If a participant cannot tolerate the drink initially, they will be given a second attempt at ingestion. If after two attempts they cannot ingest the entire item, they will be removed from the study and a replacement participant will be recruited.

Aim 2 will be an extension of Aim 1 in which all participants from Aim 1 will receive empagliflozin study drug or placebo for 12 weeks and then return for repeat testing. Participants stratified by VAT (high vs. low) will be randomized to either treatment or placebo using a random number generator (0-100, <http://www.random.org>) followed by the creation of numbered envelopes; \leq median will be assigned to treatment and $>$ median will be assigned to placebo. The minimum approved dose of empagliflozin (10 mg tablet daily by mouth taken in the morning with or without food) will be used in Aim 2 of this study; this dose was chosen to minimize the chances of adverse events (specifically hypoglycemia, dehydration, and urinary tract infections) while still maintaining efficacy in clinical trials and preliminary data. We expect that this dose will be well tolerated, with the most common side effects being urinary tract infection or yeast infection (in women).

Outcome variables:

[U-¹³C₃] glycerol enrichment in plasma blood glucose over time will be measured by nuclear magnetic resonance spectroscopy.

4. Study Procedures:

Study procedures are outlined below. Study procedures will be performed at baseline and then repeated after 3 months of study drug administration. There will also be two (2) interval visits during which study participants will meet with the study coordinator to review study drug adherence, obtain the next month's supply of study drug, and perform surveillance for any adverse effects.

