- The research materials that will be used for this proposal include demographic records and data (age, sex, weight, height, body mass index, abdominal MRI and dual x-ray absorptiometry imaging data currently collected and maintained in the Dallas Heart Study database), blood samples, and urine samples (females capable of pregnancy only). The blood and urine specimens will be taken at the time of study procedures and processed immediately. No samples will be stored. The database records that will be utilized include age, sex, race, cardiometabolic risk factor status, and data generated from blood tests and imaging phenotyping as part of the DHS study protocol.
- Prospective data to be obtained include current age, weight, height, waist circumference, hip circumference, calculated body fat percentage using both skinfold thickness at 7 different anatomical sites and bio-impedance analysis, a brief medical history, blood samples, and a urine pregnancy test (females only).
- For Aim 2, the FDA-approved drug, empagliflozin 10 mg by mouth daily, will be administered to those participants randomized to drug treatment. A matching placebo will be administered to participants not randomized to empagliflozin treatment. Both active drug and placebo will be obtained from the manufacturer (Boehringer-Ingelheim).
- No member of the study team will have access to individually identifiable private information about human subjects in the DHS. The DHS study coordinators have access to this information but are not part of the study team.
- Every study participant was assigned a randomly generated subject ID that is not linked to identifiable information. All data generated from a study participant is labeled with only their unique subject ID, including blood specimens and database records. The database records are kept on password protected servers in the DHS research center and managed by the study coordinators and statistical team. Investigators must have approved and authorized proposal to gain access to these data and all data transfers are managed by the database and statistical core. All analyses for this project will be conducted on site by the DHS statistical core. Measurements made during this study will be linked to participants in the database by the subject ID and merged into the database by the DHS statistical core.

9. Recruitment Methods and Consenting Process:

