14. Biostatistics – Statistical Analysis Plan:

Aim 1 Sample size calculation: Assuming 20% $^{13}\text{C}_3$ enrichment in subjects with low VAT (based on prior work), and an expected enrichment of between 15-18% among those with high VAT (SD 2%), for Aim 1 we expect to require 20 subjects per group to achieve 87% power to detect a 2% difference between groups at an alpha level of 0.05. Because we expect some patients may be deemed ineligible or withdraw consent in the interim between recruitment/informed consent is signed and undergoing study procedures, we will recruit up to a total of 50 subjects in order to ensure that 40 total subjects complete the study procedures (see sample size table). The study will be stopped after 40 subjects complete all study procedures and no further patients will be included in the study.

Variable	Mean Difference	Standard Deviation	Type 1 error (α)	Power ($1-\beta$)	Total N
----------	-----------------	--------------------	---------------------------	---------------------	---------

[U- ¹³ C ₃] glycerol enrichment	2%	2%	0.05	0.87	40
	3%	2%	0.05	0.89	20
	5%	2%	0.05	0.97	12
	7%	2%	0.05	0.89	6

Aim 1 Statistical analysis: Data will be expressed as means ± standard deviations. The primary outcome of mean [U-¹³C₃] enrichment of blood glucose at study end will be compared between high VAT and low VAT groups using the Student's t-test. Plots of [U-¹³C₃] enrichment over time for each group will be constructed to compare the trajectory of glycerol enrichment over time between groups and compared using a mixed linear model. The association between VAT and change in plasma blood glucose with glycerol challenge will be analyzed within each subject using a paired t-test and between groups by mean change in plasma glucose using the Student's t-test. The relationship between VAT and glycerol enrichment will also be modeled using linear regression and adjusted for potential confounders of age, ethnicity, family history of diabetes, triglycerides, lean mass, liver fat, abdominal subcutaneous fat mass, and biomarkers.

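### The Aim 1 groups are matched on age, sex and BMI, but the primary t-test uses none of these factors; if they predict enrichment, the test is conservative and gives up power.

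*Combined protocol and SAP*

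**What the plan says.** Matching is part of the design. Section 3 (Study Population) and section 9 (Recruitment Methods) both state: "Participants with high VAT will be selected and matched (age, sex, BMI) with an equal number of low VAT participants". Hypothesis 1 in section 1 frames the comparison in the same way, with the high-VAT group "compared with age, sex, and BMI-matched participants with low VAT". Neither section says whether matching is by individual pair or only balances the groups overall.

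Section 14 sizes Aim 1 as two independent groups: "20 subjects per group to achieve 87% power to detect a 2% difference between groups at an alpha level of 0.05", assuming an SD of 2%. Under Aim 1 Statistical analysis, mean enrichment at study end "will be compared between high VAT and low VAT groups using the Student's t-test". The plan reserves the paired t-test for within-subject comparisons. A supplementary linear regression of enrichment on VAT is "adjusted for potential confounders of age, ethnicity, family history of diabetes, triglycerides, lean mass, liver fat", then abdominal subcutaneous fat mass and biomarkers. That list omits sex and BMI. A mixed linear model for the enrichment curves is also planned, without a list of its terms.

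**The concern.** Matching makes the two groups alike on age, sex and BMI. If those factors predict enrichment, the difference in group means varies less from sample to sample than it would between two independent samples. An unpaired, unadjusted t-test does not see this. It estimates its error from the full within-group variance, including the part that matching has already balanced out. The standard error is then too large, confidence intervals are too wide, the true type I error is below 5%, and power is given up. The trial would bear the effort of matching within the extreme VAT deciles without collecting the precision that matching can bring.

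**Working it through.** **Inputs.** From section 14: 20 per group, difference 2 percentage points, SD 2 points, two-sided alpha 0.05. Assumed, because the documents give no figure: r, the share of within-group enrichment variance explained by age, sex and BMI, taken from 0 to 0.3.

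**1. Reproduce the plan's figure.** For an unpaired t-test, SE = 2 × √(2/20) = 0.632, noncentrality = 2/0.632 = 3.16, df = 38. Noncentral t power is 86.9%, against the stated 87%. The other rows of the sample size table also reproduce as unpaired tests:

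| Difference | Total N | Unpaired power | Stated |
|---|---|---|---|
| 3% | 20 | 88.7% | 89% |
| 5% | 12 | 97.3% | 97% |
| 7% | 6 | 88.6% | 89% |

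A paired test with zero correlation gives 85.1%, 84.6%, 92.8% and 61.2% for the four rows, so it does not fit the table. The wording therefore does not conceal a paired test.

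**2. Effect of matching on the planned test.** The true SE of the difference is 2 × √(1−r) × √(2/20), while the t-test goes on estimating about 0.632. The ratio is 1/√(1−r).
- r = 0.1: true SE = 0.632 × √0.9 = 0.600; ratio 1.05.
- r = 0.3: true SE = 0.632 × √0.7 = 0.529; ratio 1.20.

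**3. Size and power.** The t-test columns come from 4,000,000 draws of its pooled variance under matching. The adjusted model (three covariates, df = 40 − 5 = 35) uses noncentral t with residual SD 2√(1−r). The paired test (df = 19) uses noncentral t with SD of differences 2√(2(1−r)).

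| r (assumed) | t-test size | t-test power | Adjusted power | Paired power |
|---|---|---|---|---|
| 0 | 5.0% | 86.9% | 86.7% | 85.1% |
| 0.01 | 4.9% | 87.0% | 87.1% | 85.4% |
| 0.1 | 3.9% | 88.1% | 90.0% | 88.5% |
| 0.2 | 3.0% | 89.3% | 93.0% | 91.8% |
| 0.3 | 2.1% | 90.7% | 95.7% | 94.8% |

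The adjusted model breaks even with the t-test at r of about 0.01. A strictly paired test breaks even at about 0.08, where both have 87.8% power.

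**4. Confidence interval half-width.**
- t-test: 2.024 × 0.632 = 1.28 points.
- Adjusted, r = 0.1: 2.030 × 0.600 = 1.22 points.
- Adjusted, r = 0.3: 2.030 × 0.529 = 1.07 points.

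**5. Does the form of matching matter?** Trials were simulated with age, sex and BMI (60,000 per setting) under exact 1:1 matching, loose 1:1 matching (correlation 0.9 on age and BMI) and group matching without pairs. In all three, the adjusted model held its size at 4.9–5.1%, with power of 86.7–86.9% at r = 0, 89.8–90.1% at r = 0.1 and 95.6–95.8% at r = 0.3. Under group matching at r = 0.3, pairing participants arbitrarily gave 88.3%, below the unpaired 90.6%. Covariate adjustment is therefore the safer choice while the form of matching is unstated.

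**The case against.** The best defence is that the planned test meets its target in every scenario above: its power starts at 86.9% and rises with r. That is correct, and it makes this an efficiency point.

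Next, r is unknown. All participants are obese, non-diabetic and aged 30–65, and the VAT deciles are stratified by age and sex. This restriction could keep r small. At r = 0.1 the gain is only 1.9 points of power and 0.06 points of half-width. This stands as a limit on the size, but the adjusted model needs r of only about 0.01 to break even.

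Third, section 14 expects 15–18% enrichment in high VAT against 20% in low VAT, a difference of 2 to 5 points. At 2.5 points the t-test and adjusted model have 97.7% and 98.2% power at r = 0.1, and 98.7% and 99.6% at r = 0.3. The power gain is thus under 1 point once the difference reaches 2.5. However, 2 points is the difference the plan itself sizes for, and if the truth were 1.5 points at r = 0.3 the gap would be about 66% against 79%. The gains in interval width and in type I error do not depend on the true difference.

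Fourth, the terms of the mixed model are unspecified, so they might include the matching factors. The regression's lean mass and subcutaneous fat terms also overlap with BMI. Both remarks are fair, but neither changes the primary test.

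Finally, if matches are lost, the t-test moves back towards its nominal 5% size, so the sizes shown assume that the matching balance holds.

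**Conclusion.** The point holds in its conditional form. The design matches on three factors and the Aim 1 primary test uses none of them. If those factors predict enrichment, the test is conservative: at r = 0.1 it gives up 1.9 points of power (90.0 − 88.1), and at r = 0.3 it gives up 5.0 points (95.7 − 90.7) with an interval about 19% wider than needed (1.28/1.07). These figures rest on an assumed r, on matching that holds, and on the plan's own difference and SD. The planned analysis is not invalid and the sample size is not wrong. The change is still worth making, because the possible loss from adjusting is far smaller than the possible gain.

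**What to change.** - State in sections 3 and 14 whether matching is 1:1 or by group.
- Make the Aim 1 primary analysis a linear model of enrichment on VAT group with age, sex and BMI as covariates, fixed before enrichment data are analysed. The t-test can remain as a supportive analysis.
- If matching is 1:1, a mixed model with a random pair effect is an alternative. The linear model has the advantage of keeping participants whose match is lost. This matters because section 3 (Intervention) says of participants who cannot finish the glycerol drink that "they will be removed from the study and a replacement participant will be recruited", without saying that the replacement must be matched.
- Adding sex and BMI to the supplementary regression is optional, since that model is already large for 40 participants.

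The cost is SAP wording. Section 8 already lists the variables among the research materials: "demographic records and data (age, sex, weight, height, body mass index". If the factors turn out to be unrelated to enrichment, the adjusted model loses about 0.2 points of power (86.7% against 86.9%). A strictly paired test would lose about 2 points (85.1%), which is one reason not to choose it.

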0855			Collect 40ml blood sample in purple top and 1ml blood sample for blood sugar. YSI Result: _____ / _____ mg/dl
0915 -0930			Prepare for subjects receiving [U-13C3]glycerol in ½ cup filtered water: _____ kg x 0.05 gm/kg x 1 ml/1.302 gm = _____ ml Lot#: _____ Exp: n/a
0930			Have subject drink Glycerol. Follow with 1 cup filtered water to rinse bottle.
1000 +30			Collect 1ml for blood sugar and 40ml blood sample in purple top tubes. YSI Result: _____ / _____ mg/dl
1030 +60			Collect 1ml for blood sugar and 40ml blood sample in purple top tubes. YSI Result: _____ / _____ mg/dl
1100 +90			Collect 1ml for blood sugar and 40ml blood sample in purple top tubes. YSI Result: _____ / _____ mg/dl
1130 +120			Collect 1ml for blood sugar and 40ml blood sample in purple top tubes. YSI Result: _____ / _____ mg/dl
1200 +150			Collect 1ml for blood sugar and 40ml blood sample in purple top tubes. YSI Result: _____ / _____ mg/dl

Advanced Imaging Research Center

eIRB File #: 012015-064

Visceral Adiposity and Diabetes: Translating Form to Function Using Imaging

Subject Name:		Visit Date:	
Scheduled Time	Actual Time	Initials	AIRC Outpatient Procedure
1230 +180			Collect 1ml for blood sugar and 40ml blood sample in purple top tubes. YSI Result: _____ / _____ mg/dl
			Discontinue peripheral IV line after last blood sample obtained.
			Obtain vital signs. BP: _____ / _____ P: _____ T: _____ °F R: _____
			Provide lunch.
			Perform MRI scan if indicated
			On Study Day 1 Provide Emagliflozin/Placebo and Instructions.
			Discharge subject from AIRC.

Advanced Imaging Research Center eIRB File #: 012015-064 Visceral Adiposity and Diabetes: Translating Form to Function Using Imaging				
Study Time	Plasma (Pre) (40ml)	Glucose (1ml)	NMR (40ml)	Comments
				Arrive @ AIRC Start IV x 1
-60 (Pre)	X	X		
0				Glycerol consumed
+15		X	X	
+30		X	X	
+60		X	X	
+90		X	X	
+120		X	X	
+150		X	X	
+180		X	X	
				D/C IV & provide lunch
Tubes	10ml purple top tube x 1	1ml microfuge tube	10ml purple top tube x 4	
Processing	On ice → spin → plasma in small vial → REFRIGERATOR for [name]/[name]	IMMEDIATELY spin → run → record result → plasma in cryo vial for [name]/[name]	On ice → spin → plasma divide into 3 10ml plastic vials → REFRIGERATOR for [name]/[name]	

Glycerol Study Procedure Grid

VISIT 2 and VISIT 3 STUDY MEDICATION COMPLIANCE FORM

DID SUBJECT RETURN UNUSED AND/OR EMPTY MEDICATION CONTAINERS?

YES NO

If no, comment below:

Date of Last Dose Dispensed: ____/____/____
Day Mon Year

Total Number of Tablets Dispensed at last visit: _____

Total Number of Tablets Returned Today: _____

Last Dose Kit #: _____ Last Dose Lot #: _____

COMPLIANCE % = $\frac{\text{TOTAL NUMBER OF TABLETS USED}}{\text{TOTAL NUMBER OF TABLETS REQUIRED PER PROTOCOL}} \times 100$
_____ / _____ X 100 = _____

Is Subject compliant with Medication? YES NO

If no, comment below and counsel/educate subject again:

If medication compliance percentage is <80%, please re-educate subjects. The subject can be withdrawn from study after 2 visits of medication noncompliance. The principal investigator should be notified for each subject's visit of not meeting medication compliance. It is up to the discretion of the principal investigator to allow the subject to remain in the study.

MEDICATION RE-DISPENSED YES NO

If no, comment below:

Kit #: _____ Lot#: _____ Expiration Date: _____

NUMBER OF TABLETS DISPENSED? _____

MEDICATION DOSAGE GIVEN TO AND REVIEWED WITH SUBJECT YES NO
